10.1.5 Adverse Events Leading to Treatment Discontinuation

AEs leading to treatment discontinuation will be captured in the eCRF AE page. Besides treatment discontinuation, other consequences include drug interrupted, dose reduced, delayed, and increased will also be collected.

A summary of TEAEs leading to premature discontinuation of treatment by SOC and PT will be presented by treatment group.

10.1.6 Adverse Events of Special Interest (AESI)

AESIs include infusion reactions, hyperglycemia, hearing impairment, new onset inflammatory bowel disease and exacerbation of inflammatory bowel disease.

Infusion reactions will be collected on the AE eCRF form; hyperglycemia will be captured via standard MedDRA query (SMQ) narrow term "Hyperglycaemia/new onset diabetes mellitus"; hearing impairment will be captured via sub-SMQ term "Hearing impairment" (under SMQ "Hearing and vestibular disorders") and high level term (HLT) term "Hearing losses"; and new onset inflammatory bowel disease and exacerbation of inflammatory bowel disease will be captured via HLT term "Colitis (excl infective)".

A summary of TEAEs of special interest by SOC and PT will be presented and corresponding AESI listing will be provided

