Safety and Tolerability Objectives To assess safety and tolerability of TEPEZZA versus placebo based on: 

1. Adverse events (AEs)

2. AEs of special interest (AESIs) (infusion reactions, hyperglycemia, hearing impairment, new onset inflammatory bowel disease and exacerbation of inflammatory bowel disease)

3. Vital signs

4. Visual acuity

5. Clinical safety laboratory evaluations (hematology, fasting chemistry, thyroid function tests and glycated hemoglobin [HbA1c])

	

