**Safety and Tolerability Endpoints**

1. The incidence of treatment-emergent adverse events (TEAEs), serious AEs (SAEs), TEAEs resulting in premature discontinuation of treatment and AESIs (infusion reactions, hyperglycemia, hearing impairment, new onset inflammatory bowel disease and exacerbation of inflammatory bowel disease).
2. The incidence of  $\geq$ Grade 3 TEAEs.
3. The change from Baseline to each scheduled visit in vital signs (blood pressure, heart rate, respiratory rate and temperature).
4. The results of best-corrected visual acuity.
5. The incidence of  $\geq$ Grade 3 fasting glucose values.
6. The change from Baseline to each scheduled visit in laboratory evaluations (hematology and fasting chemistry [including thyroid panel and HbA1c]).

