#### 8.4 Safety and Tolerability Objectives

To assess safety and tolerability of TEPEZZA versus placebo based on:

1. AEs
2. AEs of special interest (AESIs) (infusion reactions, hyperglycemia, hearing impairment, new onset inflammatory bowel disease and exacerbation of inflammatory bowel disease)
3. Vital signs
4. Visual acuity
5. Clinical safety laboratory evaluations (hematology, fasting chemistry, thyroid function tests and HbA1c)

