#### **9.5.3.1.1.5 Adverse Events of Special Interest**

Based on previous clinical experience in TFD, the following will be AESIs for this trial:

- Infusion reactions
- Hyperglycemia
- Muscle spasms
- Hearing impairment
- New onset inflammatory bowel disease and exacerbation of inflammatory bowel disease

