### **Risk of Muscle Spasms**

Among teprotumumab-treated patients, *Muscle spasms* was the most commonly reported TEAE in clinical trials of Active TED (Double-Masked Treatment Period: 26.2% teprotumumab compared to 7.0% placebo; Open-Label Extension Trial: 41.3%). All events were non-serious and the majority were mild in intensity.

If possible, avoid medications known to cause muscle spasms or muscle toxicity, such as diuretics or statins. If muscle spasm occurs, evaluate for other causes of muscle spasm, such as electrolyte abnormalities and dehydration.

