This statistical analysis plan (SAP) describes the statistical analysis methods and data presentations to be used in tables, listings, and figures (TLFs) of the primary analysis and follow-up analysis for Study HZNP-TEP-403. The primary analysis is planned after all patients complete the week 24 visit assessments in the double-masked treatment period or withdraw from the study prior to Week 24. The follow-up analysis is planned after all patients complete the 30-day follow-up period or terminate early from the study during the follow-up period. The SAP is

based on protocol: administrative change 1 to Protocol number: HZNP-TEP-403 V4.0 (Amendment 3.0), dated on 15 December 2022 by Horizon Therapeutics U.S.A., Inc.

2. Objectives

The overall objective is to investigate the efficacy, safety and tolerability of TEPEZZA® in comparison to placebo in treating patients with chronic (inactive) TED.

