10.1 Adverse Events

Adverse events will be coded using MedDRA version 24.0. AEs that occur during Screening and prior to dosing on Day 1 will be considered pre-treatment AEs. TEAEs for the double-masked treatment period is defined as AEs with onset date on or after the first dose of study drug during the double-masked treatment period prior to receiving the first dose of TEPEZZA during open-label treatment period for patients who entered open-label treatment period, or through 3 weeks (21 days) after the last dose of study drug during the double-masked treatment period for patients who did not enter open-label treatment period. TEAEs for open-label treatment period defined as AEs with onset date on or after first dose of TEPEZZA during the open-label treatment period through 3 weeks (21 days) after last dose of TEPEZZA during the open-label treatment period. All analyses for TEAEs will be split to TEAEs reported during the double-masked treatment period and open-label treatment period separately. The follow-up AE reporting period begins 3 weeks (21 days) after the last dose of study drug through completion of the follow-up period.

An overall summary of all TEAEs including the number and percentage of patients experiencing at least one occurrence of a TEAE, serious TEAEs, treatment-related TEAEs, treatment-related serious TEAEs, TEAEs resulting in study drug discontinuation, TEAEs of special interest, TEAEs leading to death along with the summary of National Cancer Institute Common Terminology Criteria for Adverse Events (NCI-CTCAE) grade 3 or higher will be provided.

Additionally, AEs and SAEs reported during the follow-up period after each treatment period will be presented by SOC and PT separately.

All AEs, AEs with CTCAE Grade 3 or higher, SAEs, AEs leading to discontinuation of study drug, AE of special interest, and deaths will be presented in separate by-subject listings.

Signs and symptoms associated with Infusion reaction and anaphylaxis will be recorded and included in a by-subject listing.

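### Muscle spasms is an AESI in one section of Protocol V5.0 but in no other AESI list there or in the SAP, so the planned AESI outputs would leave it out

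*SAP*

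**What the plan says.** Protocol V5.0, section 9.5.3.1.1.5, sets out the AESIs for the trial in five bullets, one of which is "Muscle spasms". A risk paragraph later in that section names it as the commonest treatment-emergent event on teprotumumab in the active-TED trials, at "26.2% teprotumumab compared to 7.0% placebo" in the double-masked period.

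The other AESI lists in the same protocol version are shorter. The safety objectives in the Synopsis give "AEs of special interest (AESIs) (infusion reactions, hyperglycemia, hearing impairment, new onset inflammatory bowel disease and exacerbation of inflammatory bowel disease", and the Synopsis safety endpoints, section 8.4 and section 9.6.1.4 name the same events. Muscle spasms is in none of them.

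The SAP states in its Introduction that it is based on "administrative change 1 to Protocol number: HZNP-TEP-403 V4.0 (Amendment 3.0), dated on 15 December 2022". Its section 10.1.6 says: "AESIs include infusion reactions, hyperglycemia, hearing impairment, new onset inflammatory bowel disease and exacerbation of inflammatory bowel disease". Sections 2.4 and 3.2.4 agree. Section 10.1.6 then gives a capture rule for each listed category: the AE eCRF form for infusion reactions, and MedDRA queries or high level terms for the others. It gives no rule for muscle spasms. Two sets of outputs rest on this definition: the AESI summary and AESI listing, and the special-interest row of the overall summary in section 10.1, whose contents include "TEAEs resulting in study drug discontinuation, TEAEs of special interest, TEAEs leading to death".

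**The concern.** AESI incidence is a named safety endpoint in Protocol 9.6.1.4. What gets reported for it depends on which protocol list the programmer follows, and the list carried into the SAP is not the one in the protocol's AESI definition section.

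The omitted event is unlikely to be neutral between arms. The protocol's own figures put it at nearly four times the placebo frequency on drug (26.2 / 7.0 = 3.7). Leaving it out would probably lower the count of patients with any AESI more on TEPEZZA than on placebo, so the between-arm contrast in the AESI outputs would look smaller than under the protocol's definition.

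The open-label period is different. Every patient there receives TEPEZZA and the summaries are descriptive only, so the effect is under-counting with no placebo contrast to distort.

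**Working it through.** **Step 1. Compare every AESI list in current text.** Amendment-log text is not counted.

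| Place | Muscle spasms listed? |
|---|---|
| Protocol 9.5.3.1.1.5 | Yes |
| Protocol Synopsis, safety objectives | No |
| Protocol Synopsis, safety endpoints | No |
| Protocol 8.4 | No |
| Protocol 9.6.1.4 | No |
| SAP 2.4 | No |
| SAP 3.2.4 | No |
| SAP 10.1.6 | No |

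In the protocol, one list includes it and four do not. In the SAP, none of three includes it. The protocol's summary of changes explains the cause: muscle spasms was added to 9.5.3.1.1.5 in V5.0 as a deliberate AESI revision, and the addition did not reach the objectives or endpoints. SAP section 13 (Changes in the Planned Analysis) records no difference on AESIs.

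**Step 2. Expected patients left out, double-masked period.** The plan gives no figure of its own to reproduce. Inputs are the planned arm sizes of 38 and 19 (Protocol 9.6.7) and the active-TED rates of 26.2% and 7.0% (Protocol 9.5.3.1.1.5). The assumption is that these rates carry over to chronic TED.

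- TEPEZZA: 38 × 0.262 = 9.96, about 10 patients.
- Placebo: 19 × 0.070 = 1.33 patients.
- If the TEPEZZA rate were only 10% to 15%: 38 × 0.10 = 3.8 to 38 × 0.15 = 5.7 patients. The chance that at least one TEPEZZA patient is affected, 1 − (1 − p)^38, is then 0.98 to 0.998.

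**Step 3. Effect on the overall row for any AESI.** Some patients with muscle spasms will have another AESI and be counted anyway. If the two are independent, the understatement is (1 − other-AESI rate) × muscle spasm rate. The documents give no other-AESI rates for this trial, so those below are assumptions chosen to show the range.

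| Other-AESI rate (TEPEZZA / placebo) | Understated on TEPEZZA (points) | Understated on placebo (points) | Between-arm shift (points) |
|---|---|---|---|
| 10% / 10% | 0.9 × 26.2 = 23.6 | 0.9 × 7.0 = 6.3 | 17.3 |
| 30% / 30% | 0.7 × 26.2 = 18.3 | 0.7 × 7.0 = 4.9 | 13.4 |
| 50% / 50% | 0.5 × 26.2 = 13.1 | 0.5 × 7.0 = 3.5 | 9.6 |
| 50% / 10% | 0.5 × 26.2 = 13.1 | 0.9 × 7.0 = 6.3 | 6.8 |

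With muscle spasm rates half as high (13.1% and 3.5%), the shifts halve: 8.6 (10% / 10%), 4.8 (50% / 50%) and 3.4 (50% / 10%) points.

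**The case against.** The strongest reply is that the SAP does what it says. It declares V4.0 as its base, and its list matches the endpoint definition in Protocol 9.6.1.4, which is the section that says what is analysed. On that view the fault is an inconsistency in the protocol plus version lag, and calling the result an under-count presumes that 9.5.3.1.1.5 governs. The description of the SAP is correct. But the contradiction inside V5.0 stands whatever the SAP's base. The summary of changes also shows that adding muscle spasms was intended, which is good reason to treat 9.5.3.1.1.5 as the current definition.

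A second reply is that little is lost. Muscle spasms would still be counted by SOC and PT in the general TEAE tables, in the tables by relationship and severity, and in the listing of all AEs. No hypothesis test is applied to safety data. The protocol describes the earlier events as non-serious and mostly mild. All of this stands and limits the weight of the point. It does not supply the AESI summary, the AESI listing or the overall row. Nor does it settle, before treatment codes are seen, which related terms count as muscle spasms.

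A third reply is that the percentage-point shifts rest largely on assumed rates. That is fair. The firmer statement is the expected patient count, which needs only the assumption that active-TED rates carry over.

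**Conclusion.** The point holds. Protocol V5.0 gives two different AESI lists, and the SAP outputs built on the shorter one would be incomplete against the protocol's AESI definition. About 10 of 38 TEPEZZA patients and 1.3 of 19 placebo patients would have an AESI absent from those outputs in the double-masked period if active-TED rates apply. The row for any AESI would move by less than those counts suggest: a between-arm shift of 6.8 to 17.3 points over the scenarios shown, or 3.4 to 8.6 points if spasm rates are half as high. These shifts also assume independence from other AESIs, and they are illustrations rather than predictions. No figure is claimed for the open-label period. This is a safety-reporting defect that should be corrected. It does not touch efficacy or error control.

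**What to change.** 1. In the protocol, bring the AESI lists in the Synopsis (objectives and endpoints), section 8.4 and section 9.6.1.4 into line with section 9.5.3.1.1.5.
2. Re-base the SAP on Protocol V5.0.
3. Add muscle spasms to SAP 2.4, 3.2.4 and 10.1.6, with a MedDRA search definition stated in 10.1.6, so that it feeds the AESI summary, the AESI listing and the special-interest row of the overall TEAE summary.
4. Do this before the double-masked database lock, because Protocol 9.4.8 and SAP 5.2 allow the sponsor to be unmasked after it.

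The cost is protocol and SAP wording plus one more category in tables that are already planned. Adverse events are already collected and MedDRA-coded, so no new data are needed.

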### 9.3 Selection of Trial Population

#### 9.3.1 Inclusion Criteria

Eligible patients must meet provide all the following criteria:

1. Written informed consent.
2. Male or female at least 18 years old at Screening.
3. Initial diagnosis of TED ≥2 years but <10 years prior to Screening. Clinical diagnosis of stable, chronic (inactive) TED, as determined by patient medical records indicating a CAS ≤1 in both eyes for at least 1 year prior to Screening or all of the following:
  - a. no progression in proptosis for at least 1 year prior to Screening
  - b. if patient has history of diplopia due to TED, no progression in diplopia for at least 1 year prior to Screening
  - c. no new inflammatory TED symptoms for at least 1 year prior to Screening.
4. CAS ≤1 at the Screening and Baseline Visits.
5. Proptosis >3-mm increase from the patient's baseline (prior to diagnosis of TED), as estimated by treating physician and/or proptosis >3 mm above normal for race and gender.
6. Patients must be euthyroid with the patient's baseline disease under control or have mild hypo- or hyperthyroidism (defined as free thyroxine and free triiodothyronine levels <50% above or below the normal limits) at Screening. Every effort should be made to correct the mild hypo- or hyperthyroidism promptly and to maintain the euthyroid state for the full duration of the trial.
7. Does not require immediate surgical ophthalmological intervention and is not planning corrective surgery/irradiation during the course of the trial.
8. Diabetic patients must have HbA1c ≤8.0% at Screening.
9. Patients with a history of inflammatory bowel disease, ulcerative colitis or Crohn's disease must be in clinical remission for at least 3 months, with no history of bowel surgery within 6 months prior to screening and no planned surgery during the trial. Concomitant stable therapies for inflammatory bowel disease without modifications in the 3 months prior to Screening are allowed.

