#### 9.3.3.1 Discontinuation of Patients from Treatment

The primary reason for discontinuation from trial drug should be recorded on the eCRF using 1 of the following categories:

- AE. The patient experiences an AE that imposes an unacceptable risk to the patient's health, or the patient is unwilling to continue because of an AE. Patients who discontinue trial drug due to an AE will remain in the trial unless they withdraw from the trial for another reason. AEs requiring permanent trial drug discontinuation per the protocol include:
  - A drug-related anaphylactic reaction as defined by Sampson criteria (see Appendix 17.3 for clinical criteria).
  - Diagnosed or suspected inflammatory bowel disease (e.g., diarrhea with or without blood or rectal bleeding associated with abdominal pain or cramping/colic, urgency, tenesmus or incontinence for more than 4 weeks without a confirmed alternative diagnosis OR endoscopic or radiologic evidence of enteritis/colitis without a confirmed alternative diagnosis).
- Lack of Efficacy. Discontinuation of trial drug due to lack of efficacy is at the discretion of the Investigator or patient and may occur if the Investigator determines that trial drug administration is not benefiting the patient. Patients who discontinue trial drug due to

lack of efficacy will remain in the trial unless they withdraw from the trial for another reason.

- Lost to Follow-up. The patient does not return to the clinic for scheduled assessments and does not respond to the site's attempts to contact the patient.
- Withdrawal by Patient/Guardian. The patient wishes to withdraw from trial drug. The clinical site should attempt to determine the underlying reason for the voluntary withdrawal and document it on the eCRF
- Trial Terminated by Sponsor. The Sponsor, IRB or regulatory agency terminates the trial.
- Pregnancy.
- Death.
- Completed. The patient completed treatment.

Patients who prematurely discontinue trial drug prior to Week 21 of the double-masked Treatment Period or who enter the open-label Treatment Period and discontinue trial drug prior to Week 45 of the open-label Treatment Period will return to the clinic, undergo the scheduled End-of-Treatment assessments (with the exception of the **CCI** [REDACTED]

**CCI** [REDACTED] and enter the Follow-up Period. Patients who discontinue due to an AE should be followed until resolution or stabilization of the AE, or an adequate explanation for the event is obtained.

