#### **Risk of New Onset or Exacerbation of IBD**

- In Phase 2 TED01RV, 2 teprotumumab-treated patients with a history of IBD reported serious TEAEs (*Diarrhoea* in 1 patient and *Inflammatory bowel disease* in 1 patient) that led to discontinuation of trial drug. Based on these serious events and the fact that a placebo patient with Crohn's disease did not experience these types of events, patients with a history of IBD are either excluded from current trials or must be in clinical remission.
- Patients who experience progressive and persistent diarrhea or other IBD symptoms, such as bloody stools or abdominal pain, should undergo prompt evaluation to exclude new onset or exacerbation of preexisting IBD or other serious conditions. If possible, medications known to cause diarrhea, such as laxatives and magnesium shall be avoided. If new onset or exacerbation of IBD is suspected, teprotumumab shall be discontinued.

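### The SAP identifies the inflammatory bowel disease AESI through one colitis HLT, so a patient stopped for the protocol's symptom-defined suspected IBD may not be counted

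*SAP*

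**What the plan says.** **Search rule.** SAP 10.1.6 states that new onset and "exacerbation of inflammatory bowel disease will be captured via HLT term" *Colitis (excl infective)*. It adds no standardised query, preferred-term list or investigator flag for IBD. In the same paragraph, hyperglycemia is found by a narrow SMQ, hearing impairment by a sub-SMQ plus an HLT, and infusion reactions through the AE form. SAP 10.1 states: "Adverse events will be coded using MedDRA version 24.0".

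**Stopping criterion.** Protocol 9.3.3.1 lists among the events requiring permanent discontinuation: "Diagnosed or suspected inflammatory bowel disease (e.g., diarrhea with or without blood or rectal bleeding associated with abdominal pain or cramping/colic". The description goes on to urgency, tenesmus and incontinence. It requires these symptoms to last more than 4 weeks with no other diagnosis confirmed. The alternative limb is endoscopic or radiologic evidence of enteritis or colitis, again with no other diagnosis confirmed.

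**Basis for the risk.** Protocol 9.5.3.1.1.5 reports that in Phase 2 "2 teprotumumab-treated patients with a history of IBD reported serious TEAEs", one *Diarrhoea* and one *Inflammatory bowel disease*, and that both led to discontinuation. It gives these events as the reason that "patients with a history of IBD are either excluded from current trials or must be in clinical remission".

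**Population and endpoint.** Under Protocol 9.3.1, patients with a history of IBD, ulcerative colitis or Crohn's disease may enter but "must be in clinical remission for at least 3 months". The incidence of AESIs, naming both new-onset and exacerbated IBD, is a safety endpoint in Protocol 9.6.1.4 and SAP 3.2.4.

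**The concern.** The protocol acts on suspicion and symptoms, while the SAP counts by a diagnosis-level coding group. When IBD is suspected but not established, an investigator may reasonably record what was observed, such as diarrhoea or rectal bleeding. The patient is then permanently stopped under the protocol's IBD criterion, yet the coded term may not fall in the HLT that defines the AESI.

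At stake is whether the IBD row of the AESI summary means what a reader will take it to mean. A zero there would be read as no diagnosed or suspected IBD on treatment. Under the present rule it would mean only that no event was coded to the colitis HLT. Because the trial admits patients with IBD in remission, exacerbation is a realistic possibility.

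**Working it through.** The plan states no figure on this point, so the check sets the rules side by side and follows a record through them.

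1. **How a suspected case would be recorded.** Protocol 9.5.3.1.2 asks investigators to group signs and symptoms under one diagnosis whenever possible, and its example depends on the investigator being confident of that diagnosis. Suspected IBD is the situation in which such confidence may be lacking. Recording by symptom is therefore foreseeable, though it need not be usual.

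2. **Whether the search finds it.**
   - Recorded as IBD or as colitis: taken to be inside the HLT and counted.
   - Recorded as diarrhoea or lower-GI bleeding: taken to be outside the HLT and not counted.

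   Both lines are assumptions. The documents name MedDRA 24.0 but do not print its hierarchy. The HLT's name, which denotes a disease group and not a stool symptom, supports them, and a look in the v24.0 browser settles them. Where enteritis terms fall should be checked at the same time.

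3. **Whether another route recovers it as an AESI.** SAP 10.1.6 gives none. Protocol 9.3.3.1 records the discontinuation reason in the category AE and shows no sub-code for the IBD criterion, so the discontinuation record does not identify these patients either.

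4. **Where the event still appears.** It appears by SOC and preferred term in the TEAE table (SAP 10.1.1), and in the SAE table (10.1.4) and the discontinuation table (10.1.5) where it qualifies. It is also in the by-subject AE listing (10.1), and medical history is listed by subject (7.2). None of these outputs is planned to connect a diarrhoea row with IBD history or with the suspected-IBD criterion.

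5. **The two Phase 2 events as an illustration.** Under the assumption in step 2, the rule retrieves *Inflammatory bowel disease* and not *Diarrhoea*, that is 1 of 2. The exact 95% interval for 1/2 runs from 1 − √0.975 = 1.3% to √0.975 = 98.7%, so this is no estimate of sensitivity.

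6. **Scale of one event.** With the planned 38 TEPEZZA and 19 placebo patients, a single event is 1/38 = 2.6% or 1/19 = 5.3% of an arm. This holds for any single event and says nothing about how often one would be missed.

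**The case against.** The case for leaving the rule alone has several parts.

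- **The coding hierarchy is not in the documents.** This stands, and the point is conditional on the browser check.
- **The AESI is a diagnosis, and a diagnosis-level search is a legitimate choice.** Hyperglycemia is also searched narrowly. This stands as a defence of the HLT as the narrow search. It does not explain why the AESI output should differ from the criterion on which the same protocol stops patients.
- **The Phase 2 *Diarrhoea* event is not said to have been an IBD exacerbation.** This stands. The protocol uses it as evidence for the risk and as grounds for the entry restriction, no more.
- **The SAP was written to protocol Version 4.0, and the Phase 2 narrative was added to 9.5.3.1.1.5 by Amendment 4.** True, but the main mismatch is with 9.3.3.1, which is not among the sections listed as changed in that amendment.
- **Suspected IBD needs more than 4 weeks of unexplained symptoms or objective evidence, and 9.5.3.1.1.5 calls for prompt evaluation.** Many such cases should end with a diagnosis on the record. This narrows the gap without closing it.
- **Nothing is lost from the report.** This stands, and with about 57 patients a careful reader could cross-check the listings by hand. What is at stake is the AESI classification.

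A reader might infer that the search misses half of all cases, or that it biases the TEPEZZA rate toward zero. The documents support neither. Two events cannot give a sensitivity. The same rule applies to both arms, and the HLT, by its name, could also take in non-infective colitis that is not IBD, so the net direction is unknown.

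**Conclusion.** The concern holds as a mismatch between the SAP's search and the protocol's own criterion. A patient permanently stopped for protocol-defined suspected IBD, but recorded by symptom, would be absent from the IBD AESI summary and listing while still appearing by preferred term elsewhere.

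The conclusion rests on two assumptions: that diarrhoea and lower-GI-bleeding terms lie outside the HLT in MedDRA 24.0, and that some suspected cases will be recorded by symptom. The number of patients affected and the net direction of any error cannot be derived from the documents. Safety data are summarised without hypothesis tests (SAP 10), so no inferential result is affected. The change is worth making because AESI incidence is a named endpoint and the remedy is cheap.

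**What to change.** In SAP 10.1.6:

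- Keep *Colitis (excl infective)* as the narrow search, after confirming in the MedDRA 24.0 browser which bowel terms it contains.
- Pre-specify a supplementary broad search with a fixed term list: diarrhoea and lower-GI-bleeding terms in patients with a history of IBD, and the same terms in any patient when the event is serious or leads to discontinuation.
- Have a medical reviewer, masked to treatment, examine the retrieved records and flag those that meet the suspected-IBD description in Protocol 9.3.3.1. This review is needed because no documented field identifies that criterion.
- Complete the term list and the masked review before the Week 24 database lock. Report narrow and broad counts by arm after unmasking, with the flagged events identified in the AESI listing.

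The cost is a paragraph of SAP text, an added table row and a brief review of a few AE records, similar to the manual review that SAP 8.3 already uses for restricted medications. The downside is that the broad count will include some diarrhoea unrelated to IBD, which is why it stands beside the narrow count and does not replace it. No eligibility, dosing or stopping rule changes.
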